7.1.7. Safety Evaluation Method

[figure not shown]
1 month, 3 months, 6 months after operation, it is mainly recorded of the severity, incidence date, duration time, treatment and results for all the adverse events and serious adverse events by clinical symptom safety and adverse event assessment.

The method and time selection for evaluation, recording and analysis of safety parameter: the monitoring of subjects' vital sign including before operation, during operation, and before discharge; adverse events monitoring including during operation, immediately after operation, before discharge and follow up for safety.

7.2. Trial Procedure

- Written informed consent shall be signed.
- Check up of exclusion criteria
- Case Inclusion
- Intervention operation (intervention operation and implanting occluding devices)
- Follow up evaluation

I. Trial Flow Chart

II. Trial Flow Chart

Research Stages	Screening	Treatment/follow up period					
	Pretreatment	Hospitalization Treatment Period			Follow up 1	Follow up 2	Follow up 3
Time window	Before operation Within 15 days	Operation Record:	Immediately after operation.	Between Post operation and pre-discharge	1 months ± 7 days	3 months ± 15 days	6 months ± 30 days
Informed Consent	√						
Inclusion/Exclusion Criteria	√						

Demographic Data	√						
Vital Signs	√	√		√			
Medical History	√						
Medication Record (History)	√	√	√	√	√	√	√
Blood Routine:	a			√			
Urine Routine	√ ^a			√			
Blood Biochemistry	√ ^a			√			
Blood coagulation	√ ^a						

Urine Pregnancy	√ ^a						
Electrocardiogram	√ ^a	√	√	√	√	√	√
Ultrasonic Cardiogram	√ ^a	√	√	√	√	√	√
Chest X-rays	√ ^a			√			
Adverse Events		√	√	√	√	√	√

a. If the blood routine, urine routine, blood biochemistry, blood coagulation, urine pregnancy, electrocardiogram, Chest X-rays, ultrasonic cardiogram have already been carried out within 15 days before signing of informed consent, they can serve as baseline assessment, needless of repetition; for urine pregnancy, it is only necessary for women of child bearing age.

b. Medication records are only necessary for recording of anti-coagulation, anti-biotics and anti-virus drugs relevant to trials;

For testing items not required by the current protocol however with relevant prescription in the medical institutions, it is carried out of inspection according to the requirements in details of the medical institutions.

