7.1.2. Trial Method Selection and Their Rationale

The current trial applied perspective, multiple centered, randomized controlled non-inferiority clinical trial. It is evaluated of the safety and efficacy of completely degradable occluder system in clinical application, with the ventricular septal defect occluder manufactured by Shanghai Shape Memory Alloy Co., Ltd as the clinical trial control product. It is evaluated of the safety and efficacy of occluder surgical intervention delivery devices in clinical application, with the occluder intervention delivery devices manufactured by Shanghai Shape Memory Alloy Co., Ltd as the clinical trial control product. The primary endpoint index for evaluating occluder surgical intervention delivery devices is that it can be released when the occluder is delivered to the lesion location during operation; and the primary endpoint index for evaluating completely degradable occluder system is the success rate at month 6, which is evaluated for efficacy through ultrasonic cardiogram.

7.1.3. Measures for reduction and avoidance for deviation.

- 1) Before research initiation, the sponsor should carry out relevant training for researchers participated in the current research, and ensuring that the researchers sufficiently understand the research flow, and skillful in the operation of research instruments; during the course of research, the researchers should carry out operation strictly according to the operating methods and specification in the research protocol, and the clinical research monitor should do well of the quality control and monitoring work, and ensure that the researchers carry out operation and implementation strictly according to the research protocol. It is implemented of the measures mentioned above during the entire research procedures, to reduce the losses or operation errors;
- 2) It applied strict randomized trial design, to avoid the selection deviation in treatment. After the trial started, when the subjects meet the inclusion criteria for testing, the researchers shall log on to the central randomizing system for randomized grouping.

- 3) Subjects are screened for inclusion and exclusion strictly according to the clinical diagnostic criteria in trial protocol, to reduce the selection deviation;

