7.1.5. Selection of subjects

7.1.5.1. Inclusion Criteria

- (1) The subjects and (or) their legal guardians should know the nature of the current research, and consent to participate in the current clinical trial according to all the clauses of the current research. They must sign the informed consent approved by the ethics commission, and agree to receive the post-operative treatment protocol, and finish the follow up and relevant inspection required by the follow up, according to the follow up requirements.
- (2) Aged between one year and 60 years old, with body weight higher than 10kg, male or not pregnant women;
- (3) Effective shunt mouth for VSD is between 3mm and 14mm;
- (4) The upper margin of VSD is no less than a distance of 3mm from the right coronary valve of aorta, without aortic right coronary valve shedding into VSD and aortic regurgitation above moderate degree;

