7.3.2. Implanting Procedures

Systemic anesthesia trachea cannula, operation area sterilization, routine operation list. Make a skin incision of a length between 2cm and 3cm subcostal, sequentially incise the skin, subcutaneous tissues and muscle layer, and partly cleave the sternum, cut open the pericardium and suspend, to expose the right ventricle, and suture a pad type pouch on it. Puncture the puncturing needle through the center of the pad, send the guiding steel wire into the cardiac cavity, make sure that the guiding steel wire is through the VSD, and then withdraw the puncturing needle, deliver the delivery sheath along the guiding steel wire through the VSD, withdraw the delivery sheath inner core and the guiding steel wire. Select the occluder of proper diameter according to the measuring results, in general the selected occluder diameter is 2 to 4 mm larger than the defect diameter detected with ultrasonic measurement. Load the occluder into the loading sheath, discharge all the air bubbles in the occluder through the side hole on the hemostatic valve. Connect the loading sheath with the delivery sheath, deliver the occluder, during the operation, it is used of esophagus ultrasonic cardiogram real time monitoring, open the left ventricular side umbrella disc, make the occluder umbrella into plane shape, withdraw it to the left ventricle opening of the defect, and fix the delivery device, withdraw the sheath, release the occluder right ventricle side umbrella disc. Push and pull the occluder back and forth, if the location is fixed, the ultrasonic inspection detected occluder would not influence the aortic valve, tricuspid valve and the neighboring tissue structure, release the delivery device tong head, and release the occluder. Since the degradable occluder is woven by degradable high molecular materials, the elasticity is inferior than the common NiTi alloy occluder, after complete release, it can only restore to about 70% of the original form, therefore, it is necessary to pull the safety rope, and contact the lower disc surface of the occluder with the outer sheath tube mouth, through pulling the safety rope, restore the occluder completely into the original form. Finally, withdraw the safety rope, release the delivery device handle dead lock piece, release the occluder, and withdraw both the delivery devices and outer sheath from the heart.

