13.3 Serious adverse events

Serious adverse events refers to events that occur during clinical trial, such as events causing hospitalization or prolonged hospitalization, disability, affecting work ability, endangering life or death, permanent injury or physical dysfunction, injury requiring treatment and intervention, fetal diseases, fetal death or congenital malformation, etc.

Selective operation, combined operation and other expected diseases that have been clearly identified in the pre-enrollment diagnosis are not considered as serious adverse events.

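### The only scheduled urine pregnancy test can be 15 days old at operation (30 in the worst case), and no later test is required although non-pregnancy is an inclusion criterion

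*Combined protocol and SAP*

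**What the plan says.** All references are to the combined protocol and SAP.

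- **Eligibility.** Inclusion criterion (2) in section 7.1.5.1 takes subjects aged 1 to 60, "with body weight higher than 10kg, male or not pregnant women".
- **Schedule.** In the section 7.2 flow chart, the "Urine Pregnancy" row has one tick, in the screening column, marked with footnote a. That column's time window reads "Before operation Within 15 days". Consent and the inclusion/exclusion check are ticked in the same column and nowhere else.
- **Reuse rule.** Footnote a names eight tests, including urine pregnancy. If they "have already been carried out within 15 days before signing of informed consent, they can serve as baseline assessment, needless of repetition". Its last clause limits the pregnancy test to the relevant women: "for urine pregnancy, it is only necessary for women of child bearing age".
- **Randomization.** Section 7.1.3, item 2: "when the subjects meet the inclusion criteria for testing, the researchers shall log on to the central randomizing system for randomized grouping".
- **Grouping time.** Section 7.1.5.4 sets the time of surgical implantation as the grouping time point.

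**The concern.** Pregnancy status can change between screening and surgery, unlike most of what is checked at baseline, and a test taken very early in pregnancy may be negative. A rule that lets an older result stand without repetition suits a chest X-ray better than a pregnancy test.

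As the protocol is written, a woman who conceives after the test, or whose pregnancy was too early to detect, can go on to the procedure in section 7.3.2. It begins "Systemic anesthesia trachea cannula, operation area sterilization, routine operation list" and continues with partial division of the sternum and an implant delivered through the right ventricle. Section 13.4 describes heparin during the operation, and the schedule has a chest X-ray before discharge. Section 13.3 lists "fetal diseases, fetal death or congenital malformation" among serious adverse events, so the protocol already treats fetal harm as an outcome to be reported.

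**Working it through.** The check is date arithmetic plus a search for any later test.

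**Inputs**

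- W = 15 days: screening window before operation (section 7.2, column heading).
- F = 15 days: look-back before consent (section 7.2, footnote a).
- Number of pregnancy tests scheduled: one, at screening. None is ticked at operation, after operation, before discharge, or at months 1, 3 and 6.

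The protocol gives W and F but does not state the resulting age of the test at operation.

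**Maximum age of the test at operation**

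1. The column heading binds every result, including reused ones: maximum age = W = 15 days.
2. Footnote a extends the window: maximum age = F + W = 15 + 15 = 30 days. This needs a test on the earliest day allowed before consent and consent on the earliest day allowed before operation.
3. With a negative result required within 72 hours before operation: maximum age = 72 / 24 = 3 days.

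**Is a later test required elsewhere?**

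| Place | What it provides | Requires a later test? |
|---|---|---|
| 7.1.5.2, exclusion criteria | Pregnancy not listed; item 6 leaves unsuitability to the researcher's judgement | No |
| 7.1.5.4, grouping time | Checks are general data, vital signs, history, diagnosis and past treatment | No |
| 7.2, closing sentence | Tests the protocol does not require follow the hospital's own rules | No |
| 7.3.1, preparation | Refers to cardiac surgical preparation; no test named | No |

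Sections 7.1.3 and 7.1.5.4 together show the gap. A site may randomize once the criteria are met, and the criteria check is ticked only at screening. The moment that counts as grouping is the operation, and nothing in the protocol refreshes the pregnancy result in between.

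**The case against.** **Fifteen days is the firmer figure.** Footnote a is attached to ticks inside a column limited to 15 days before operation. Section 12.3 requires consent before any research procedure, so the footnote may serve only to let routine pre-consent results count as baseline, without widening the column. A reader might infer that the protocol simply allows a 30-day-old test. The text does not settle that, and 30 days also needs both extremes at once. This objection stands: 15 days leads, and 30 is a conditional worst case.

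**Non-pregnancy arguably has to hold at implantation.** Section 7.1.5.4 places grouping at the operation, so a site operating on an outdated result would not be acting in the spirit of the criterion. That is fair, but the section prescribes no test that would show the criterion is still met.

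**Hospitals may retest anyway.** Cardiac surgical preparation and local rules may include a repeat test. They may, but the protocol makes neither a condition, so verification of its own criterion is left to local practice in a multicentre trial.

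**The text has reading limits.** The first of the two flow charts is not reproduced in the text available, and the blood routine row of the second has lost a tick. The pregnancy row shows its single tick, and nothing suggests that a later one was lost.

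**No document sets a shorter interval.** This is true. The 72 hours is a proposal, and the case for it rests on safety and low cost rather than on a rule the protocol breaks.

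**Conclusion.** The point holds as a low-severity safety improvement. The only scheduled pregnancy test can be up to 15 days old at operation, or up to 30 if footnote a's look-back adds to the screening window. Footnote a waives repetition and no section requires a later test.

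Three stronger readings are tempting and are not supported:

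- *A stated reduction in risk.* A percentage would need the lag between conception and a positive urine test, which the documents do not give. It would also describe a worst-case window rather than a risk. None is claimed.
- *A number of women exposed.* The documents do not say how many of the 108 subjects will be women of child-bearing age.
- *A threat to the trial's result.* The endpoint, the 8% margin, the sample size, the analysis sets and the non-inferiority rule do not depend on this test.

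The conclusion assumes that the flow chart's pregnancy row was read correctly and that the protocol text, rather than local practice, defines what is required.

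**What to change.** Remove urine pregnancy from the reuse list in footnote a, keep the screening tick, and add:

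> *For women of child-bearing age, a negative urine pregnancy test result obtained within 72 hours before the operation is required. The researcher logs on to the central randomizing system only after this negative result. If the operation is then delayed beyond 72 hours after the test, the test is repeated, and a positive result at any time means the operation is not performed.*

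Add the matching tick to the pregnancy row. The other seven tests in footnote a stay as written.

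**Cost.** Usually one extra urine test per woman of child-bearing age. It is two if her pre-consent result would have been reused or the operation is delayed; only both together would add a further repeat. No bloods, ECG, echocardiogram or X-ray is repeated. The amendment is minor but needs the signatures and ethics approval described in section 12.1.

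**Side effect.** A woman who tests positive after randomization because of a delay would be randomized but untreated. Section 8.9 defines the full analysis set by randomization and device use, so she would fall outside it and should be reported as such. The change shortens the gap without closing it, since a very early pregnancy can still be missed.

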7.3. Operation Procedure and Instrument Application Norm

7.3.1. Preparation before operation

It is prepared according to the cardiac surgical operation.

7.3.2. Implanting Procedures

Systemic anesthesia trachea cannula, operation area sterilization, routine operation list. Make a skin incision of a length between 2cm and 3cm subcostal, sequentially incise the skin, subcutaneous tissues and muscle layer, and partly cleave the sternum, cut open the pericardium and suspend, to expose the right ventricle, and suture a pad type pouch on it. Puncture the puncturing needle through the center of the pad, send the guiding steel wire into the cardiac cavity, make sure that the guiding steel wire is through the VSD, and then withdraw the puncturing needle, deliver the delivery sheath along the guiding steel wire through the VSD, withdraw the delivery sheath inner core and the guiding steel wire. Select the occluder of proper diameter according to the measuring results, in general the selected occluder diameter is 2 to 4 mm larger than the defect diameter detected with ultrasonic measurement. Load the occluder into the loading sheath, discharge all the air bubbles in the occluder through the side hole on the hemostatic valve. Connect the loading sheath with the delivery sheath, deliver the occluder, during the operation, it is used of esophagus ultrasonic cardiogram real time monitoring, open the left ventricular side umbrella disc, make the occluder umbrella into plane shape, withdraw it to the left ventricle opening of the defect, and fix the delivery device, withdraw the sheath, release the occluder right ventricle side umbrella disc. Push and pull the occluder back and forth, if the location is fixed, the ultrasonic inspection detected occluder would not influence the aortic valve, tricuspid valve and the neighboring tissue structure, release the delivery device tong head, and release the occluder. Since the degradable occluder is woven by degradable high molecular materials, the elasticity is inferior than the common NiTi alloy occluder, after complete release, it can only restore to about 70% of the original form, therefore, it is necessary to pull the safety rope, and contact the lower disc surface of the occluder with the outer sheath tube mouth, through pulling the safety rope, restore the occluder completely into the original form. Finally, withdraw the safety rope, release the delivery device handle dead lock piece, release the occluder, and withdraw both the delivery devices and outer sheath from the heart.

7.3.3. Instrument Application Norm

(1). Research group Instrument

Name: Completely degradable occluder system;

Manufacturing unit: Shanghai Shape Memory Alloy Co., Ltd

Storage Conditions: Stored in temperature lower than -10C, without corrosion gas and in clean environment.

Validity Period: One year

The Name: Occluder surgical intervention delivery devices

Manufacturing unit: Shanghai Shape Memory Alloy Co., Ltd

Storage conditions: The current product shall be stored in cool, dry, clean, well-ventilated environment without corrosive gases, and it shall be avoided of direct sun glaring and rain and snow falling during transportation procedures.

Validity Period: Three years

(2). Control group Instrument

The Name: Ventricular septal defect occluder (Product already registered by Shanghai Shape Memory Alloy Co., Ltd);

Manufacturing unit: Shanghai Shape Memory Alloy Co., Ltd

Storage conditions: The current product shall be stored in clean environment with relative humidity no higher than 80%, without corrosive gas, dry and well-ventilated.

Validity Period: Three years

The Name: Occluder intervention delivery devices (Product already registered by Shanghai Shape Memory Alloy Co., Ltd).

Manufacturing unit: Shanghai Shape Memory Alloy Co., Ltd

Storage conditions: The current product shall be stored in dry, clean, well-ventilated environment without corrosive gas.

Validity Period: Three years

(3). Package

The packages from inside to outside are respectively: Blister box, double layer dialysis bag (Paste with label on the second layer), alumina foil bag (Paste with label on the surface).

(4). Label

- ① The Name and Address of the sponsor
- ② Identify inner content and package operation batch no and/or codes

- ③ “Used in Clinical Trial” mark
- ④ Storage Requirements
- ⑤ Application time limits (Expiry Date)

(5). Instrument Preservation and Management

All the instruments used in the current research shall be preserved in the clinical research trial unit, which shall establish strict testing instrument preservation and distribution registration system, and dedicated personnel by the sponsor shall directly deliver the testing instruments into the various research center, and the research center shall establish sophisticated trial instrument receiving procedures with the implementer, and the record shall include: Date, Quantity, Batch No/Serial No, Expiry Date, etc.

The sealed instrument package shall be preserved under prescribed temperature and humidity conditions, each research unit shall select the instrument manager, and establish the dedicated “Application Record Form for clinical trial medical instrument”, and register the subjects’ name Pinyin abbreviation, and randomized no, application date, and signature by the instrument manager, etc.

The trial instrument can only be taken for application by the authorized research personnel. Each instrument taken out from the preservation location shall be recorded and signed by the research personnel. Only sealed instrument package can be returned into the cabinet, and make the corresponding records.

After trial termination the trial sponsor shall collect all the unused instrument, and responsible for the recovery of unused research instrument and carry out centralized processing. When the research finishes, it should be counted of all the materials.

(6). Application Instruction

It should be applied of the instrument according to the prescription in compliance with the suggestion by the company in the current protocol. In order to avoid the adverse outcome, please read the manual carefully before application, in particular, it must take heed of all precautions and matters in need of attention.

The product is applicable for MRI.

7.4. Monitoring Planning

Monitoring Frequency: First case monitoring, for each 5 cases of patients grouped shall be monitored once; at the same time, since the grouping of the first case of patient, it shall be monitored routinely for every 3 months.

Monitoring content:

- ① Confirm the subjects according to the inclusion criteria for grouping;
- ② Check up the CRF according to the original medical history of the subject and original records and research medical history, to ensure the accuracy of the records, which should be in time and integral;
- ③ Inspect the researcher's document folder in the center, to ensure that the content shall be integral without mistakes;
- ④ It shall be inspected of the trial operation to be complied with the protocol, as well as the requirements in GCP;
- ⑤ It shall be inspected that the trial is carried out of operation according to the requirements by the ethics commission;
- ⑥ It shall be inspected of the procedure norm for acquisition of informed consent;
- ⑦ If the above content is deviated from the protocol, formulate the protocol breach report and submit to the ethics commission.

8. Statistical Consideration

